The fatigue and dyspnea video's will be viewed back-to-back and the edema video will be added for patients with a history of edema. There are 4 versions of each video: (1) based on race (Caucasian and African-American) and sex (male and female)—to promote symbolic modeling— by patients who look like video models (as stated in the introduction). Scripts for each video were developed jointly by [name], Director of Media and Education for Wellflix, Inc. and [name] PhD, principal investigator and clinical nurse specialist in HF. Content includes recognition and assessment of fatigue, dyspnea and edema and specific actions to take to reduce the danger signs or prevent worsening (dietary sodium and/or fluid restriction, physical activity/exercise and contacting the doctor).

Overall video viewing time for all 3 videos is 9:50 minutes; the fatigue and dyspnea videos that all intervention patients will view are 6:50 minutes:

- *Fatigue* is 2:20 minutes + end text list= 3:00 minutes;

NCT-03657459

- *Dyspnea* is 1:40 minutes + dyspnea “yes” or “no” management (2 options; patient selects the option that matches current status) = 3.50 minutes
- *Edema* is 2:40 minutes + end text list= 3:00 minutes;

During hospitalization, videos will be loaded into an iPAD and will be viewed through the iPAD.

Patients have an opportunity to view videos post-discharge as desired and able. *Post discharge*, videos can be in 2 ways: (1) via the Wellflix, Inc. site at www.wellflix.net/DangerSignsCC or (2) by DVD player (DVD created by Wellflix, Inc for this research), for patients who have DVD player capability and prefer this method.

NOTE, at/after 180-day follow up data are collected, *usual care group* patients will be offered access to Wellflix, Inc. videos used in this research study via mailing of a handout sheet developed specifically for them (that contains the web address and a note of encouragement to view the videos.

Outcomes and Measurement

HCRU. Includes all-cause and HF-related hospitalization, ED visit, death, cardiac transplantation, or VAD placement at 30-, 90-, and 180-days \pm 6 days in both groups. Data will be retrieved from medical records when available or via telephone call to patients.

- Patients will receive a calendar to keep track of HCRU events in-between phone calls.
- Research nurses will use a case report form to record HCRU events

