Patient characteristics and medical history at baseline. Standard patient characteristics that are used in many research studies of patients with HF, will be used in this research as they span themes of interest and provide global information about participants. Items include height and weight, highest education, comfort living on current household income, current signs and symptoms of HF, comorbid conditions and billing data retrieved from Cleveland Clinic billing database (age, race, gender, marital status, discharge disposition, and length of hospital stay). The *Charlson Comorbidity Index* will be used to collect medical comorbidity history. This index was developed to classify comorbid conditions which might change the risk of mortality.²⁴⁻²⁹ The score will be categorized into 3 groups (score of 1-2 = 1; 3-4 = 3; 5 or more = 5). In one study with 33,940 patients with ischemic heart disease, the grouping demonstrated a strong relationship with mortality rate.²⁹ In 2011, the tool was reduced from 19 items to 12 items and each item was re-scored based on morbidity and mortality of medical conditions in the current era of medical therapies.³⁰ This data will also be used to describe the sample groups for similarity in acuity.

Video Watching Experiences in-hospital and at 30 day follow-up (intervention group only). A 3-item, investigator-developed survey will assess video watching characteristics: total number of watching’s, caregiver/family member video watching *in the hospital*, and

NCT-03657459

caregiver/family member video watching *in the post discharge* period, up to 30 days. Items use choose-the-best-response options.

Data Collection

Medical records will be assessed for inclusion and exclusion criteria before approaching patients. Research personnel will explain the study in a patient's room (in non-private rooms, a curtain will be drawn to separate beds and enhance confidentiality). After received verbal informed consent, patients will complete baseline data that includes assessment of functional status, dyspnea, fatigue and self-efficacy for managing symptoms immediately before hospitalization. Administration of the functional status, dyspnea and fatigue questionnaires will be randomly changed for each participant to allow for counterbalancing, since there item themes may have overlap/be similar. Baseline data collection should take 10 minutes or less.

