Patient characteristics will be summarized overall and by randomized group using frequencies and percentages for categorical factors and means and standard deviations for continuous measures. First occurrence HCRU use (**all-cause and HF-related**) will be compared using Pearson chi-square tests. Time to first HFCU use will be summarized using Kaplan-Meier estimates, and compared using log-rank tests and Cox proportional hazards models. Total HCRU use will be compared using Poisson regression models. Linear mixed effect models will be used to evaluate trends in functional, dyspnea, fatigue, and self-efficacy measures over time and, if trends significantly differ, comparisons within time point will be performed. Secondary analyses will use similar methods to compare patients in the video group, stratified by video viewership, on the same outcomes. If appropriate, exploratory analyses will also be performed, comparing the above outcomes between treatment groups, adjusting for any patient characteristics that differ between randomized groups. Analyses will be performed using SAS software (version 9.4; Cary, NC), and an overall significance level of 0.05 will be assumed for all endpoints. Comparisons between the 3 subgroups of patients in the video group will use Bonferroni corrected significance criteria to preserve the overall error rate when making multiple comparisons.

Feasibility

The main campus of Cleveland Clinic has a high volume of HF discharges each year. Other hospitals in the system have moderate volumes of HF discharges, and are less likely to have patients who meet exclusion criteria due to enrollment in another research study or non-ambulatory NYHA FC IV (advanced) HF. Electronic medical records allow for review of data on events that occur in *all* system hospitals and regional medical practice ambulatory care sites; decreasing the need to rely on patient recall of HCRU.

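### Aim 3 compares self-selected viewing groups within the video arm with no covariates planned, while the plan's only covariate adjustment is kept for the randomized comparison

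*Combined protocol and SAP*

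**What the plan says.** The Analyses section sets out the arm-versus-arm methods first. First occurrence of HCRU "will be compared using Pearson chi-square tests". Time to first event is "compared using log-rank tests and Cox proportional hazards models". For counts, "Total HCRU use will be compared using Poisson regression models". The four questionnaire scales go into linear mixed models. The viewing comparison then gets one method sentence: "Secondary analyses will use similar methods to compare patients in the video group, stratified by video viewership, on the same outcomes".

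The next sentence holds the only covariate adjustment in the plan. It is exploratory, conditional on being appropriate, and concerns "comparing the above outcomes between treatment groups, adjusting for any patient characteristics that differ between randomized groups". A Bonferroni criterion is added for the three viewing subgroups.

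On how viewing arises, the Intervention section says: "Patients have an opportunity to view videos post-discharge as desired and able". The outcome list names three viewing exposures: total number of viewings, family viewing in hospital, and family viewing after discharge. A three-item survey records them up to 30 days.

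Baseline data include "highest education, comfort living on current household income, current signs and symptoms of HF, comorbid conditions", plus age, race, gender, marital status, the Charlson index and the four baseline scales. None of these is assigned to Aim 3.

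**The concern.** Randomization balances the two arms. It does nothing for viewing groups formed afterwards inside one arm. Patients who re-view may differ in motivation, severity or cognition, and family viewing needs a family member who is available. If those traits also predict HCRU, the contrast mixes them with any effect of viewing.

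The protocol's own Introduction makes this plausible. It reports that self-care adherence goes with better understanding of signs and symptoms and with better outcomes. An engaged patient could do better whether or not re-viewing helps.

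A Pearson chi-square test cannot carry a covariate. Cox, Poisson and mixed models can, but the plan does not say that they will. So adjustment is planned where it is least needed and not where it is most needed. Bonferroni limits chance findings and does not address confounding. Intention-to-treat protects only the comparison of arms. The Limitations section notes that patients may never re-view, but does not mention self-selection.

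At stake is whether a viewing difference gets read as evidence that repeat or family viewing works.

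**Working it through.** **1. The plan's own figures.** The sample-size section gives 329 per group, two-sided 0.05, and control rates of 28% (30 days) and 46% (90 days).

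- Video-arm rate at 30 days: 0.28 × (1 − 0.33) = 0.1876, about 18.8%.
- Video-arm rate at 90 days: 0.46 × (1 − 0.25) = 0.345.
- Power at 30 days, pooled-variance test: mean rate 0.2338; null SE = √(2 × 0.2338 × 0.7662 / 329) = 0.0330; alternative SE = √((0.28 × 0.72 + 0.1876 × 0.8124) / 329) = 0.0328; (0.0924 − 1.96 × 0.0330) / 0.0328 = 0.845, so power is 80.1% (stated 80%).
- Power at 90 days, same formula: 85.4% (stated 85%).
- Enrolment: 329 / 0.9 = 366 per group.

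These reproduce and are not in dispute. No power or sample size is given for Aim 3.

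**2. Events available in the video arm.** 0.1876 × 329 = 62 at 30 days; 0.345 × 329 = 114 at 90 days.

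**3. Illustration of confounding.** The documents give no confounder strength, so every input here is an assumption:

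- Viewing has no effect on outcome.
- 329 evaluable video patients split evenly into 164 viewers and 164 non-viewers.
- A baseline prognostic index is normal with SD 1. Viewers' mean is lower (better) by d SD.
- logit(risk) = a + b × index, with a solved so that the average risk is 18.8% or 34.5%.

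The rejection rate is that of a two-sided two-proportion test at 0.05 and at 0.05 / 3 = 0.0167.

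Worked case, 90 days, b = 0.7, d = 0.3: risks 32.35% v 36.65%, risk ratio 0.88. Null SE = √(2 × 0.345 × 0.655 / 164) = 0.0525; alternative SE = 0.0524. Lower tail: (0.0430 − 1.96 × 0.0525) / 0.0524 = −1.14, probability 0.127. Opposite tail: 0.003. Total: 13%.

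| Time | b | d (SD) | Spurious risk ratio | Rejects at 0.05 | Rejects at 0.0167 |
|---|---|---|---|---|---|
| 30 days | 0.5 | 0.2 | 0.92 | 6% | 2% |
| 30 days | 0.7 | 0.3 | 0.85 | 11% | 5% |
| 30 days | 0.7 | 0.5 | 0.77 | 21% | 11% |
| 30 days | 0.9 | 0.5 | 0.72 | 29% | 16% |
| 90 days | 0.5 | 0.2 | 0.94 | 7% | 3% |
| 90 days | 0.7 | 0.3 | 0.88 | 13% | 6% |
| 90 days | 0.7 | 0.5 | 0.81 | 28% | 15% |
| 90 days | 0.9 | 0.5 | 0.78 | 38% | 23% |

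If viewers were the sicker group, the same rejection rates would arise with the risk ratio inverted.

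**4. Does adjustment help?** A second model used one binary confounder: risk ratio 1.5 or 2, with a low-risk share of 60% v 40% or 70% v 30% in viewers and non-viewers. Across the settings simulated, the unadjusted chi-square at 0.05 rejected in about 6-21% of trials at 30 days and 8-42% at 90 days. A Mantel-Haenszel test stratified on the confounder rejected in 4.3-5.4%. That holds when the confounder is measured.

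**5. What adjustment cannot do.** Post-discharge viewing accrues over the same 30 days as the primary endpoint, so an early event can cut viewing short. In a simulation with no effect and no confounding, where viewing stops counting at the event and 30-70% of patients would otherwise re-view by day 30, the chi-square rejected in 67-99% of runs. This is a separate bias. Family viewing in hospital takes place before discharge and escapes it, yet remains open to confounding.

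**The case against.** Several points on the other side stand.

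- **The wording is already associational.** Aim 3 and Hypotheses 3a to 3c all speak of association. A reader might infer that all three claim a causal mechanism. They do not: 3a, the HCRU hypothesis, has no causal clause; 3b cites heightened awareness; only 3c cites symbolic modeling.
- **The scales are partly covered.** Outcomes 7-10 are changes from baseline analysed by mixed models of trends, which deals in part with different starting levels. The gap is mainly in HCRU.
- **The direction is unknown.** It is tempting to say that viewers will be healthier or better supported, so the bias will flatter the videos. The documents do not establish this. The Feasibility section expects that forgetful patients can replay the videos many times, which could point the other way.
- **The edema link is unproven.** Under Intervention, "the edema video will be added for patients with a history of edema". One might infer that edema history raises the viewing count. The survey does not say whether each video is counted separately, and the Design section describes three videos for intervention patients. If the link existed and edema marked sicker patients, it would bias against viewing.
- **The split is a simplification.** The plan speaks of three subgroups, not two equal halves, and at the weak end of the illustration the inflation is small.

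It can also be said that unadjusted is an inference, since the plan never uses the word. With a chi-square for first occurrence, and adjustment mentioned only for treatment groups, it is the natural reading. None of these points supplies the missing covariates.

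**Conclusion.** The point holds in a limited form. As written, Aim 3 contrasts self-selected groups without named covariates, and its HCRU results are open to baseline confounding whose direction and size the documents cannot settle. Under the assumptions shown, false-positive rates at 0.05 run from about 6% to 29% at 30 days and 7% to 38% at 90 days; at the Bonferroni level they are about 2-16% and 3-23%. These are illustrations, not predictions.

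A reader might go further and doubt the trial's main result. That does not follow: the primary comparison is between randomized arms by intention to treat, and only outcome 11 is affected. Nor should anyone infer that adjustment makes Aim 3 causal. Family support is captured only partly, through marital status, and the timing bias remains. The change is worth making before analysis, as an improvement to a secondary aim.

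**What to change.** In the Analyses section, replace the sentence on similar methods with adjusted models for each of the three viewing exposures:

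- logistic regression for first occurrence;
- Cox regression for time to first event;
- count regression for totals;
- mixed models that include the baseline score for the scales.

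Pre-specify one covariate set from items the protocol says it collects: age, race, gender, marital status, education, income comfort, HF signs and symptoms, Charlson index, and baseline DASI, dyspnea, fatigue and self-efficacy. NYHA class and edema history are not in the baseline list, so add them only if they are recorded.

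That is twelve items for about 62 video-arm events at 30 days, or 62 / 12 ≈ 5 events per item even before counting category levels. Keep the set smaller, or use a separate propensity score for each exposure; a single score cannot serve a count and two family-viewing indicators.

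Report unadjusted and adjusted estimates side by side, as associations with residual confounding. State that baseline adjustment does not remove the overlap between post-discharge viewing and the 30-day outcome window.

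The cost is a change of wording, modest extra analysis and slightly wider intervals. No new data are needed.

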After completing baseline paperwork, patients will be randomly assigned to the usual care or usual care plus HF danger signs video education group using block randomization; with blocks of 20, to decrease the influence of external factors that could alter outcomes. The randomization assignment will be made by a QHS statistician.

After randomization to groups:

- Intervention group patients will receive usual hospital care and also, HF danger signs education via iPad by research personnel. Danger signs education can be administered at the time of enrollment. There is no need to wait until day of discharge, since HF danger sign messages are not individualized and discharge is a very busy time. Immediately prior to discharge, patients' focus may be on preparing to leave the hospital and not on education about HF, especially if patients believe that they have accurate perceptions of HF danger signals, even though in previous research, most subjects did not.
- Usual care group patients will be educated by their healthcare providers (including nurse/other caregivers). Education may include Elsevier HF videos that are shown on Cleveland Clinic hospital televisions.

A research nurse will use telephone calls or mailing methodologies to have the following 4/5 tools (40/43 items in total for usual care and intervention groups, respectively) completed at 30 ± 6 days: functional status, dyspnea, fatigue, self-efficacy for managing symptom and video watching experiences. Administration of functional status, dyspnea, and fatigue questionnaires will be randomly ordered (counterbalanced). The intervention-only group survey on video watching experiences will be administered last. It is expected that data collection will take ~ 10 minutes or less.

A research nurse will review EMRs of enrolled patients after the index (baseline) hospital discharge and at 30-, 60-, 90- and 180-days (± 6 days) for HCRU events.

- If not found in the EMR, telephone calls will be made to gather data.
- At baseline, research nurses will obtain home telephone number and the telephone number of a close relative or friend that can provide patient contact information, as needed.

NCT-03657459

Analyses

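### The exploratory adjusted analysis picks covariates by observed imbalance, so it usually omits prognostic baseline data and could admit length of stay, which is fixed after randomization

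*Combined protocol and SAP*

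**What the plan says.** Under *Analyses*, first-occurrence healthcare resource utilization (HCRU) "will be compared using Pearson chi-square tests", with no covariates. The primary endpoint, HF-related HCRU at 30 days, is of this type. Adjustment appears in one later sentence: "If appropriate, exploratory analyses will also be performed, comparing the above outcomes between treatment groups", "adjusting for any patient characteristics that differ between randomized groups". No covariate is named, and how large a difference must be to count is not stated. Baseline characteristics are to be summarized; no baseline significance tests are described.

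Under *Patient characteristics and medical history at baseline*, the items taken from billing data are "age, race, gender, marital status, discharge disposition, and length of hospital stay". The same paragraph collects the Charlson index, grouped in three levels, and cites a cohort in which the grouping was strongly related to mortality. Its stated use here is to describe how similar the groups are in acuity. *Data Collection* adds baseline functional status (DASI), dyspnea, fatigue and self-efficacy scores. None of these is prespecified as a covariate for HCRU.

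On timing, *Data Collection* says: "After completing baseline paperwork, patients will be randomly assigned to the usual care or usual care plus HF danger signs video education group". This happens during the index stay. For the intervention arm, "Danger signs education can be administered at the time of enrollment. There is no need to wait until day of discharge".

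**The concern.** The sentence raises two problems.

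First, it chooses covariates by the wrong property. What makes a covariate useful in a randomized comparison is that it predicts the outcome. Whether it happens to differ between arms is, for a true baseline variable, a matter of luck. A rule based on imbalance fixes the model only after the baseline table has been seen, and it usually leaves out variables that would have sharpened the estimate.

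Second, the pool of eligible variables is not limited to what was known at randomization. Length of stay and discharge disposition sit under a baseline heading but are complete only at discharge, after allocation and possibly after the videos. If one of them differed between arms, the rule as written would adjust for it. If that difference were partly an effect of allocation, the adjusted estimate would no longer be the effect of assignment.

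The sentence covers all the outcomes listed before it, including the primary. If the adjusted and unadjusted results disagreed, a reader could not tell whether the treatment estimate or the choice of covariates was responsible.

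**Working it through.** **1. The plan's own sample size.** Inputs from *Sample and Setting*: control rate 28%, 33% relative decrease (so 0.28 × 0.67 = 18.76%), two-sided 0.05, 80% power, Pearson chi-square.

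- Mean rate = (0.28 + 0.1876)/2 = 0.2338.
- n per arm = [1.96·√(2 × 0.2338 × 0.7662) + 0.842·√(0.28 × 0.72 + 0.1876 × 0.8124)]² / 0.0924² = 329 after rounding up. Power at 329 is 80.1%.
- 329/0.9 = 366 per arm, 732 in total.
- At 90 days, 46% against 34.5% gives 85.4%, against the stated 85%.

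All stated figures reproduce. None of them depends on the adjustment sentence.

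**2. How often the rule selects by luck.** Assumption, not in the plan: a characteristic differs if p<0.05. Each true baseline variable is then selected about 5% of the time and omitted about 95% of the time. With k independent characteristics, the chance that at least one is selected by luck is 1 − 0.95^k: 40% for k=10, 54% for k=15 and 64% for k=20. The counts, the independence and the threshold are all assumed, so this is a range rather than a property of the plan.

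**3. What the rule does to precision.** This is a simulation with 329 per arm, rates of 28% and 18.8%, and one standard normal baseline covariate of assumed strength. Tests come from logistic regression, with 6,000 runs for power and 8,000 under no effect.

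| Log-odds per SD (assumed) | Unadjusted power | Adjust only if imbalanced | Always adjust |
|---|---|---|---|
| 0.4 | 80.0% | 80.2% | 81.3% |
| 0.7 | 79.4% | 79.8% | 82.1% |
| 1.0 | 79.6% | 80.5% | 85.5% |

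The simulation standard error is about √(0.8 × 0.2/6000) = 0.5 points. Adjusting only on imbalance is close to not adjusting at all. Type I error was 4.7%, 4.9% and 4.5% under the imbalance rule, and 4.8%, 5.4% and 4.9% when always adjusting. There is no inflation.

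**4. The same gain by formula.** If the covariates explain a share R² of outcome variance, the effective size per arm is about n/(1 − R²). At a 28% event rate, an assumed AUC of 0.637 corresponds to R² = 0.047, and 0.682 to R² = 0.086.

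- 329/(1 − 0.047) = 345 per arm, power 82.0%.
- 329/(1 − 0.086) = 360 per arm, power 83.5%.

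These lie within the simulated range for always adjusting, 81.3% to 85.5%. No AUC is given in the documents.

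**5. Timing of the two doubtful variables.** Randomization follows the baseline forms, in hospital. The videos may be shown at enrollment. Total length of stay and final disposition are known only at discharge. Both are therefore settled after allocation, and no text excludes them from adjustment. Eligibility narrows disposition, since patients must be going to home, assisted living or a family member's home, and planned skilled-nursing or hospice discharge is excluded. Length of stay is the clearer case. The documents give no effect of the videos on either variable, so no bias can be computed.

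**The case against.** The strongest reply is that the sentence is labelled exploratory and applies only where appropriate. This stands, and it limits the point. A reader might infer that the primary result is exposed, or that its error rate is inflated. The documents do not support that: the primary comparison is the unadjusted chi-square on which the sample size was based, and step 3 shows no inflation even within the adjusted analysis.

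A reader might also infer that the trial loses power on its primary test. It does not. The plan claims no power for the exploratory analysis, and the gain in steps 3 and 4 would reach the primary result only if the primary test were changed, which is not proposed here.

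Nor can it be said that length of stay would bias the estimate. The intervention is 6:50 to 9:50 minutes of video, providers and unit nurses are meant to be blinded, and no mechanism linking the videos to discharge timing is described. If the videos do not affect length of stay, adjusting for it does not create bias by this route. What stands is that the plan permits the adjustment and gives no safeguard.

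Finally, the prognostic data are not excluded outright. Any of them enters if it happens to be imbalanced, and the patient-reported scores have their own mixed models. The documents link only the Charlson grouping to an outcome, and that outcome is mortality. The prognostic value of age and DASI for 30-day HF-related HCRU is an assumption.

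The exploratory label does not make imbalance a sound way to choose covariates, and this is the only adjusted between-arm analysis described.

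**Conclusion.** The point holds at modest weight. The covariate rule in the exploratory adjusted analysis should be replaced because it selects on chance imbalance, does not guarantee use of prognostic data already collected, and permits adjustment for length of stay and, less plausibly, discharge disposition.

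If a difference is read as p<0.05, a given baseline variable is omitted about 95% of the time and the precision recovered is close to nil: at most about 1 point of power over unadjusted in the simulation. A fixed set would raise power of the adjusted comparison from 80% to about 82% to 83.5%, assuming an AUC of about 0.64 to 0.68. The possible bias from a post-randomization covariate cannot be sized from the documents. The primary test, its type I error and 329 per arm stand as they are.

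**What to change.** Replace the sentence in *Analyses* with a prespecified adjusted analysis, supportive to the unadjusted chi-square, along these lines:

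- Covariates are a short fixed set known before randomization, used whatever the observed balance: for example age, Charlson group, baseline DASI and enrolling hospital (main campus or other). Hospital is not in the listed characteristics but is known at enrollment. *Feasibility* describes different patient mixes by site, and no stratification by site is stated.
- First occurrence is analyzed by logistic regression, reported as a standardized risk difference so that it sits on the same scale as the unadjusted comparison. The same covariates go into the Cox and count models.
- Length of stay and discharge disposition are not adjusted for; they may still be described by arm.
- Observed imbalance does not select covariates.

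The cost is SAP wording and a few lines of SAS, with no added patients and no new questionnaire. The one small downside is that a simple rule for missing covariate values must be written in advance.
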